The currently recommended antiplatelet treatment regimen for patients affected by acute coronary syndromes (ACS) and those undergoing percutaneous coronary intervention (PCI) consists in the combination of aspirin and a $P2Y_{12}$ receptor inhibitor [1-3]. Currently, three $P2Y_{12}$ receptor inhibitors are available for clinical use (clopidogrel, prasugrel, and ticagrelor). Among these, clopidogrel remains the most widely used to reduce recurrent ischemic events [1, 4,5,6]. However, several studies have shown that there is a broad variability in platelet-inhibitory response induced by clopidogrel, which in turn is associated with worse outcomes [7]. Variability in clopidogrel response is a multifactorial process [7]. Clopidogrel is a prodrug that requires bioactivation into its active metabolite before targeting the P2Y₁₂ receptor on blood platelets. In vivo bioactivation of the drug is a 2-step process that is closely linked to the cytochrome P450 (CYP) system [8]. The most prominent and best established genetic factor is located within the CYP2C19 gene, as the polymorphically expressed isoenzyme CYP2C19 is involved in both metabolic steps of clopidogrel's active metabolite generation [8,9]. In particular, a single-nucleotide polymorphism located within the CYP2C19 gene is a major determinant of clopidogrel responsiveness [9]. The presence of CYP2C19*2 and CYP2C19*3 LOF allelic variants is associated with a loss of enzyme function and comes along with an attenuated response to clopidogrel leading to higher risk for ischemic events [10]. CYP2C19 *2 allele is the most common LOF variant with allele frequencies of ~15% in Caucasians and Africans, and 29-35% in Asians [11].

More potent P2Y₁₂ receptor inhibitors (prasugrel and ticagrelor) have been developed and are associated with less response variability than clopidogrel and better clinical outcomes in

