Blood sampling: Peripheral venous blood samples (20 mL) will be drawn through a short venous catheter inserted into a forearm vein and collected in citrate, EDTA, and serum tubes as appropriate for assessments. The first 2-4 mL of blood will be discarded to avoid spontaneous

platelet activation. Blood sampling for PD will be performed at the following time points: prior to run-in baseline visit (24 hours after last clopidogrel dose in order to assess trough levels of platelet reactivity), after run-in (12 hours after last ticagrelor maintenance dose of run-in period), 24 hours after washout (groups A and C only), and 2, 24, 48, 72 hours and 10±3 days after randomization. For patients randomized to groups A and C, both requiring 24 hours washout from last MD, they will take their morning MD of ticagrelor after blood sample collection for their post-run-in phase and return the following morning to receive the randomized treatment (these groups will have a total of 8 blood sampling time points). Patients randomized to groups B and D will initiate their randomized treatment the same morning of the post-run-in phase visit (these groups will have a total of 7 blood sampling time points). CYP2C19 genetic status will be evaluated at baseline visit. PD assessment will include VerifyNow point-of-care testing (VN-P2Y₁₂), light-transmittance aggregometry (LTA) and whole blood vasodilator-stimulated phosphoprotein (VASP) as described below. Time points will have a $\pm 10\%$ window. Results of genetic testing will not be used for clinical decision makings on choice of antiplatelet treatment regimen to be used at the end of the study. This is because we are studying patients in stable clinical conditions who have already on maintenance clopidogrel therapy without experiencing ischemic events, which are more likely to occur in the earlier phases of treatment in the setting of PCI [10]. Moreover, routine genetic testing and modification of treatment based on results of genetic testing is a class III recommendation in practice guidelines [1,2]. An illustration of the study design is provided below. A study table summarizing protocol procedures is provided as an appendix.

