The primary endpoint is the comparison of PRU assessed by VN- P2Y₁₂ at 48 hours after switching from ticagrelor 90 mg bid to clopidogrel 600 mg LD given 24 hours after last ticagrelor MD (group A) vs. clopidogrel 75 mg MD given 24 hours after last ticagrelor MD (group C). We hypothesize that switching from ticagrelor to clopidogrel with a loading dose will have less increase in platelet reactivity than that without loading dose and the sample size was determined based on the objective of establishing superiority of this approach. Superiority will be assessed using a 95% confidence interval (CI) of the difference in mean PRU between these two groups. Under the assumption of a mean difference of 60 PRU between groups and a common standard deviation of 50 PRU, a sample size of 16 per group allows for the 95% CI with a 95% power and alpha=0.05. Considering 4 arms of treatment and a possible invalid data in 20-25% of patients due to technical issues or drop-outs, we will randomize up to a total of 80 patients to ensure complete data. We anticipate screening 100 patients to identify these 80 patients to be randomized. Secondary endpoints include comparison of PRU (other than primary endpoint) assessed by VN-P2Y₁₂, 5 and 20 µM ADP aggregation assessed by LTA and VASP-PRI in all four groups at each time points; rates of HPR according to each platelet function assay

(VN-P2Y₁₂, LTA, and VASP-PRI) in all four groups at each time point; impact of CYP2C19 LOF genetic status on PD parameters.

Statistical analysis plan

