Continuous variables will be expressed as a mean \pm SD when are normally distributed or median [IQR] when are not normally distributed. Categorical variables will be expressed as frequencies and percentages. The Kolmogorov-Smirnov test will be used to examine data distribution normality. Comparisons between categorical variables will be performed using twotailed Fisher's exact test or the Pearson's chi-square test. Student's t test, Mann-Whitney U-test and Wilcoxon test will be used to compare continuous variables when appropriate. A repeated measures analysis of variance (ANOVA) model will be used to evaluate intra-group comparisons and the overall difference between groups. An analysis of covariance (ANCOVA) method with a general linear model, using the baseline value of platelet reactivity as a covariate, will be used to evaluate all between-groups comparisons. Missing data will not be imputed. A 2-tailed p value of < 0.05 is considered to indicate a statistically significant difference for all the analyses performed. Statistical analysis will be performed by our group using SPSS v22.0 software (SPSS Inc. Chicago, IL).

Possible Discomforts and Risk

The study entails blood draws at multiple time points as indicated above. The risks of the blood draw may include faintness, inflammation of the vein, pain, bruising or bleeding at the site of the puncture. There is also a slight risk of infection from the blood draw. In clinical trials, the

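### The between-group ANCOVA adjusts for one unnamed baseline value although every patient has two PRU values before randomization; if the one used is V2, the patient's own clopidogrel response is left out

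*Combined protocol and SAP*

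**What the plan says.** The Statistical analysis plan specifies an ANCOVA by general linear model, "using the baseline value of platelet reactivity as a covariate", and says that it "will be used to evaluate all between-groups comparisons". By that wording it covers the primary A versus C comparison. The section Study endpoints and sample size calculation describes the primary analysis without mentioning adjustment: "Superiority will be assessed using a 95% confidence interval (CI) of the difference in mean PRU between these two groups".

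The Blood sampling paragraph of Research design schedules platelet function tests in all groups at two times before randomization:

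- V1, "prior to run-in baseline visit (24 hours after last clopidogrel dose in order to assess trough levels of platelet reactivity";
- V2, "after run-in (12 hours after last ticagrelor maintenance dose of run-in period".

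Research design places randomization after the run-in, so both values precede it. A third test, at V3, is scheduled "24 hours after washout (groups A and C only". It follows randomization but precedes the randomized clopidogrel.

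The word baseline does not settle which visit is meant. It is attached to the V1 visit in Blood sampling and in Table S1, and Table S1 also uses it for the PD test at V2 and at V3. The plan also says that missing data will not be imputed.

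**The concern.** The two pre-randomization values carry different information. In A and C the 48 h PRU is measured on clopidogrel, and V1 is the same patient's response to that drug. The project overview says that "there is a broad variability in platelet-inhibitory response induced by clopidogrel", and it describes less response variability with ticagrelor. V2 is the on-ticagrelor level from which the hypothesized increase in reactivity starts.

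If V2 is the single covariate, the model may leave much of the between-patient variation in clopidogrel response in the residual. That would widen the interval that decides superiority, in a comparison planned on 16 evaluable patients per arm. The missing measurement is already scheduled for every patient, and using it needs only a model term.

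**Working it through.** **Inputs from the plan.** "Under the assumption of a mean difference of 60 PRU between groups and a common standard deviation of 50 PRU"; 16 per group; alpha 0.05, two-tailed in the Statistical analysis plan; up to 80 randomized (20 per arm) to allow for 20-25% invalid data or drop-outs. At 20% loss, 20 × 0.80 = 16 per arm remain; at 25%, 15.

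**Inputs assumed.** The within-arm correlations of V1 and V2 with 48 h PRU, and with each other. The documents give none, so a range is shown.

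**Step 1: the plan's own figure.** n = 2(z_α + z_β)² × 50²/60².

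- One-sided 0.05, 95% power: 2(1.645 + 1.645)² × 0.6944 = 15.03, so 16. This matches the plan.
- Two-sided 0.05: 2(1.960 + 1.645)² × 0.6944 = 18.05, so 19 (20 with the t distribution).

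At 16 per arm, unadjusted two-sided power is 90.7% (noncentral t). That gap from 95% is a separate matter. It is given here only as a reference level.

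**Step 2: formulas for A versus C.** With k covariates and n = 16 per arm:

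- residual SD = 50√(1 − R²)
- df = 30 − k
- SE = residual SD × √(2/16) × √(29/(29 − k)), where the last factor is the expected cost of estimating the slopes
- half-width = t(0.975, df) × SE
- power from the noncentral t with noncentrality 60/SE
- for two covariates, R² = (r₁² + r₂² − 2r₁r₂r₁₂)/(1 − r₁₂²)

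**Step 3: main illustration** (V1 0.5, V2 0.2, 0.3 between them). Joint R² = (0.25 + 0.04 − 0.06)/0.91 = 0.253.

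| Covariates | R² | Residual SD | df | SE | Half-width | Power |
|---|---|---|---|---|---|---|
| V2 only | 0.040 | 49.0 | 29 | 17.63 | 36.1 | 90.8% |
| V1 only | 0.250 | 43.3 | 29 | 15.58 | 31.9 | 96.1% |
| V1 and V2 | 0.253 | 43.2 | 28 | 15.84 | 32.4 | 95.5% |

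Using V2 alone costs 96.1 − 90.8 = 5.3 points against the best single choice. Using both costs 96.1 − 95.5 = 0.6.

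**Step 4: other assumptions.**

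| V1, V2, between | V2 only | V1 only | Both |
|---|---|---|---|
| 0.7, 0.2, 0.3 | 90.8% | 99.5% | 99.3% |
| 0.5, 0.5, 0.3 | 96.1% | 96.1% | 98.1% |
| 0.5, 0.3, 0.3 | 92.2% | 96.1% | 96.0% |
| 0.5, 0.1, 0 | 90.0% | 96.1% | 95.7% |
| 0.3, 0.2, 0.3 | 90.8% | 92.2% | 91.6% |
| both useless | 89.7% | 89.7% | 88.5% |

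In the two-arm model the second covariate pays for itself once its partial correlation with 48 h PRU exceeds about 0.20. The largest loss in the table from adding it is 89.7 − 88.5 = 1.2 points.

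**Step 5: one model across four arms** (64 patients, df = 60 − k, factor 59/(59 − k), common slopes and residual SD). With both values useless, going from one covariate to two takes power from 91.1% to 90.7%, a loss of 0.4 to 0.5 points. The break-even partial correlation falls to about 0.13.

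**The case against.** The strongest reply is that one baseline covariate is an accepted ANCOVA and may already be the best choice. If the plan means V1, which Blood sampling calls the run-in baseline visit, adding V2 may give nothing. In four of the five informative rows of step 4, and in step 3, V1 alone equals or slightly beats both. This stands, and it makes the gain conditional.

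A reader might infer that the plan discards precision whichever visit it uses. The documents do not support that, because they leave the visit undefined and give no correlation. V1's predictive strength is itself an assumption: it follows at least 30 days on 75 mg, whereas the 48 h value follows a week of ticagrelor and then either a loading dose or resumed maintenance dosing.

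A reader might also credit a second covariate with the whole rise from 90.7% to about 95%. That compares two covariates with none. The plan already has one, so the fair contrast is one against two.

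The single value could also be V3 for A versus C. V3 precedes the randomized clopidogrel, but it follows randomization in an open-label trial and does not exist in B or D, so it cannot serve all the comparisons that the ANCOVA is meant to cover.

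Finally, a second covariate under the no-imputation rule can only reduce the complete cases. This also stands, and the fix has to deal with it.

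**Conclusion.** The point holds in a conditional form. The plan names one covariate for all between-group comparisons and does not say which visit supplies it, while two randomization-safe values exist in every arm. The analysis as planned is valid; the risk is lost precision if V2 is the value used and V1 predicts better.

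Under the main assumptions that loss is about 5 points of power (90.8% against 95.5% with both) and 3.7 PRU of half-width (36.1 against 32.4). If V1 is the value used, adding V2 ranges from a modest gain to a loss of about 1 point, or under half a point in a four-arm model. This asymmetry supports naming both, since the correlations are not known in advance.

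The four-arm figures assume common slopes and a common residual SD. Group D stays on ticagrelor, so that assumption should be checked.

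**What to change.** In the Statistical analysis plan, before analysis:

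1. Replace the single baseline covariate with the V1 and V2 values of the same assay, and exclude V3.
2. State that this model supplies the A versus C estimate and its 95% CI.
3. Preferably fit one model across all four arms, and say what is done if slopes or residual variances differ in D. The two-arm model is the fallback, at the costs shown in steps 3 and 4.
4. Make an explicit exception to the no-imputation rule: a missing or invalid V1 or V2 covariate takes the all-arm mean for that visit. This uses only pre-randomization data and ignores arm and outcome. It keeps every patient with a valid 48 h PRU. Outcomes remain unimputed.

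The cost is a few sentences, one extra model term, one residual degree of freedom and the fill-in exception. No new samples or patients are needed.

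### Baseline-adjusted ANCOVA with no imputation drops patients whose only gap is the baseline assay from the 48-hour A versus C comparison; the likely cost is about one power point or less, and one sentence avoids it

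*Combined protocol and SAP*

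**What the plan says.** The section on study endpoints and sample size defines the primary endpoint: "The primary endpoint is the comparison of PRU assessed by VN- P2Y₁₂ at 48 hours after switching", group A against group C. It adds: "Superiority will be assessed using a 95% confidence interval (CI) of the difference in mean PRU between these two groups". It plans 16 evaluable patients per group, allows for "a possible invalid data in 20-25% of patients due to technical issues or drop-outs", and randomises up to 80 patients over four arms, that is 20 per arm.

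The Statistical analysis plan specifies an ANCOVA by general linear model, "using the baseline value of platelet reactivity as a covariate, will be used to evaluate all between-groups comparisons". The next sentence is "Missing data will not be imputed". No fallback is given for a patient without a baseline value.

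The plan does not say which sample supplies the covariate. Groups A and C have three samples before clopidogrel starts: before run-in (V1), after run-in (V2) and after the 24-hour washout (V3). Table S1 labels the samples at both V2 and V3 as baseline.

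**The concern.** A general linear model cannot use a case whose covariate is missing. Together, the two adjacent sentences mean that each patient needs two valid assays, baseline and 48 hours, to count in the primary comparison. One failed baseline run discards an observed primary outcome.

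Declining to impute outcomes is defensible. For a covariate measured before randomisation the same rule only loses data: filling a gap with the overall mean, without regard to arm, does not bias a randomised comparison. With 16 to 20 patients per arm each outcome carries weight, and a covariate that removes cases can in principle cost more precision than it returns. LTA and VASP-PRI fall under the same model and the same rule.

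**Working it through.** **The plan's own figure.** Inputs from the sample size section: "Under the assumption of a mean difference of 60 PRU between groups and a common standard deviation of 50 PRU", and "a sample size of 16 per group allows for the 95% CI with a 95% power and alpha=0.05". With n = 2(z_α + z_β)²·SD²/Δ²:

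- One-sided 5%: 2 × (1.645 + 1.645)² × 50²/60² = 15.03, so 16 per group. The figure reproduces (power 95.3% by noncentral t).
- Two-sided 5%: 2 × (1.960 + 1.645)² × 50²/60² = 18.05, so 19 (20 by t). At 16 per group the power is 90.7%.

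The Statistical analysis plan says "A 2-tailed p value of < 0.05 is considered to indicate a statistically significant difference for all the analyses performed", so the two-sided figures are the reference below. For the allowance, 64/0.80 = 80.

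**Failure rate per sample (assumption).** Suppose 20-25% of patients have at least one invalid sample among the 7 or 8 planned, and failures are independent. The rate is then 1 − 0.80^(1/8) = 2.8% up to 1 − 0.75^(1/7) = 4.0%.

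**Patients lost, from 20 randomised per arm.**

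- At 2.8%: valid 48-hour PRU 20 × 0.972 = 19.4; both assays valid 19.44 × 0.972 = 18.9; difference 0.5.
- At 4.0%: 20 × 0.96 = 19.2; 19.2 × 0.96 = 18.4; difference 0.8.

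**Formulas.** With n per arm having a valid outcome, N patients in total having both assays, and correlation ρ between baseline and 48-hour PRU:

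- Unadjusted 95% CI half-width = t(2n−2) × SD × √(2/n)
- Complete-case ANCOVA half-width = t(N−3) × SD × √(1−ρ²) × √[(4/N)(1 + 1/(N−4))]

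**Power under the 2.8-4.0% assumption (20 per arm, difference 60, SD 50, two-sided 5%).**

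| ρ | ANCOVA, complete cases | Unadjusted |
|---|---|---|
| 0.3 | 95.5-95.9% | 95.1-95.4% |
| 0.5 | 98.0-98.3% | 95.1-95.4% |

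Simulation at about 3.5% failure per sample compares the plan's rule with a mean-filled baseline: 95.4% against 96.2% at ρ = 0.3, and 98.3% against 98.6% at ρ = 0.5. Deletion therefore costs under one point. Type I error with the filled baseline stayed near 5%.

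**When adjustment would be worse than none.** For large samples the break-even is about ρ² = m, where m is the share of patients with a valid outcome but no baseline. At 16 per arm with valid outcomes (unadjusted half-width 2.042 × 50 × √(2/16) = 36.1 PRU), complete-case ANCOVA gives a wider interval when ρ is below:

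| Baselines missing | m | ρ threshold |
|---|---|---|
| 0 of 32 | 0% | 0.19 |
| 1 of 32 | 3.1% | 0.27 |
| 3 of 32 | 9.4% | 0.37 |
| 6 of 32 | 18.8% | 0.49 |

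The first row shows the small cost of fitting a covariate at this sample size. It makes the reversal come slightly sooner than ρ² = m suggests. Two examples lie either side of the threshold. With 6 of 32 lost and ρ = 0.3, the half-width is 39.6 PRU and power 85.2%. With 3 of 32 lost and ρ = 0.5, they are 33.7 PRU and 94.1%, still better than the unadjusted 36.1 PRU and 90.7%.

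**The case against.** The strongest reply is that the plan already pays for this loss. It randomises 20 per arm so that 16 complete patients remain, and on that reading the 16 already excludes anyone without a baseline. With 16 complete cases per arm, ANCOVA power is 92.2% at ρ = 0.3 and 96.1% at ρ = 0.5, against 90.7% unadjusted. This largely stands, and it is why the working starts from 20 randomised per arm and finds a small effect. It does not show that discarding an observed outcome gains anything.

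A reader might infer that a quarter of baselines could fail, with power falling well below 90%. The documents do not support that. The allowance is stated for patients, not for each sample, and it includes drop-outs. Someone who leaves before 48 hours has no outcome to rescue, so even 3-4% per sample may be too high for baseline assay failure.

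Two further reservations stand. Deletion of incomplete cases is implied, not written. The primary inference is described as a confidence interval for a difference in means, and Student's t test is also listed, so an unadjusted primary analysis, which would lose nobody, is not fully excluded. The wording covering all between-group comparisons is the more specific rule and points to ANCOVA.

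Finally, V3 follows randomisation in an open-label trial and exists only in groups A and C. The no-bias argument, and a mean over all randomised patients, hold only if the baseline is V1 or V2.

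**Conclusion.** The gap is real and small. As written, the plan removes patients with a valid 48-hour PRU and no valid baseline from the adjusted A versus C comparison. Under an assumed 3-4% failure per sample, with failures at random, the cost is about one power point or less.

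It would be tempting to conclude that adjustment harms this trial. The documents do not support that: they give neither the baseline failure rate nor the correlation, and at the assumed rate adjustment is no worse than no adjustment at correlations of 0.3 and 0.5. Nor is there evidence of bias: with baselines lost at random, the simulated mean difference stayed at about 60 PRU. The change is optional.

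**What to change.** First, name one pre-randomisation sample, V1 or V2, as the ANCOVA baseline. Then replace the no-imputation sentence with:

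> Missing outcome data will not be imputed. A missing baseline covariate will be replaced by the mean of that baseline over all randomised patients, regardless of arm, so that every patient with a valid outcome at the time point stays in the ANCOVA.

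Apply it separately to PRU, each LTA measure and VASP-PRI. The replacement text cannot be used as worded for V3, because groups B and D have no such sample.

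The cost is a short edit to the analysis plan and one line of SPSS syntax, with no extra patients or samples. The downside is negligible: a filled case contributes its outcome but no covariate adjustment.

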- On therapy with aspirin(<100mg/day) and clopidogrel (75mg/day) for at least 30 days per standard of care
- 3) Age between 18 and 80 years old

Exclusion Criteria

- 1) History of intracranial bleeding
- 2) Known hepatic impairment (based on clinical judgment)
- 3) Active bleeding or propensity to bleed or blood dycrasia
- 4) Platelet count $< 80 \times 10^6 / \text{mL}$
- 5) Hemoglobin <10g/dL
- 6) Hemodynamic instability
- 7) Estimated glomerular filtration rate (eGFR) <30 mL/min
- 8) On treatment with oral anticoagulants
- 9) Patients with sick sinus syndrome (SSS) or II or III degree AV block without pacemaker protection

[figure not shown]
- 10) Drugs interfering CYP3A4 metabolism (to avoid interaction with ticagrelor): ketoconazole, itraconazole, voriconazole, clarithromicin, nefazodone, ritonavir, saquinavir, nelfinavir, indinavir, atazanavir and telithromizycin
- 11) Pregnant females [women of childbearing age must use reliable birth control (i.e. oral contraceptives) while participating in the study].

Research design

Patients meeting inclusion criteria will be enrolled in this prospective, randomized, openlabel study. Baseline labs obtained within the past 180 days will be considered valid for screening purposes. If baseline labs are not available, these will need to be obtained prior to considering a patient eligible for study entry (patients will have 90 days to enter the study). Eligible patients will undergo a 7±2 day run-in phase with ticagrelor after switching from clopidogrel 75mg/day to ticagrelor 180mg LD followed by 90mg bid MD. Ticagrelor dosing in this study is line with FDA recommendations [15]. After this run-in phase, patients will be randomized (1:1:1:1) into one of the four following groups: A) clopidogrel 600 mg LD 24 hours after last MD of ticagrelor, followed by 75mg daily MD; B) clopidogrel 600 mg LD 12 hours after last MD of ticagrelor, followed by 75mg daily MD; C) clopidogrel 75mg daily MD 24 hours after last MD of ticagrelor; D) continue ticagrelor MD 90mg twice daily. The FDA approved dose for clopidogrel is 300 mg loading dose and 75 mg/qd maintenance dose; however standard of care loading dose is 600 mg which is in line with practice guidelines [1-5].

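### The 5% significance label applies to every analysis, so secondary comparisons among the switching groups can be called significant without any error control; the primary comparison is not affected

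*Combined protocol and SAP*

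**What the plan says.** The section on study endpoints and sample size names a single primary comparison: PRU at 48 hours, group A against group C, judged by a 95% CI for the difference in means.

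The same section makes secondary endpoints of all other PRU comparisons and of "ADP aggregation assessed by LTA and VASP-PRI in all four groups at each time points". It adds "rates of HPR according to each platelet function assay", again for all four groups at each time point, and the effect of CYP2C19 loss-of-function status.

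The Statistical analysis plan assigns repeated measures ANOVA to within-group comparisons and to the overall group difference, and ANCOVA to all between-group comparisons. It then sets one decision rule: "A 2-tailed p value of < 0.05 is considered to indicate a statistically significant difference for all the analyses performed".

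Nowhere do the documents rank the secondary endpoints, adjust for their number, make pairwise tests depend on the overall test, or call secondary results exploratory.

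**The concern.** The rule gives every secondary p value below 0.05 the same label as the primary result. A reader of the final report could not tell a protected finding from one that emerged from many looks at the same patients.

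This matters most for timing. Groups A and B differ only in the interval since the last ticagrelor dose, and the Background says that the effect of this interval has not been explored. Yet no measure or hour is named for A versus B, so every assay at every visit is a separate chance of a significant result. The same holds for loading dose at hours other than 48, and for HPR. The section on possible benefits says that pharmacodynamic differences may prompt a larger clinical study, so a false lead would have a cost.

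**Working it through.** The documents give no number of tests and no overall error rate, so there is no figure of the plan's own to reproduce here.

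**Inputs from the documents**
- Arms: "patients will be randomized (1:1:1:1) into one of the four following groups", which gives 4 × 3 / 2 = 6 pairs (Research design).
- Group D stays on ticagrelor: "D) continue ticagrelor MD 90mg twice daily". Only the 3 pairs among A, B and C bear on loading dose and timing.
- Post-randomization times: "2, 24, 48, 72 hours and 10±3 days after randomization", that is 5 (Blood sampling; Table S1).
- Continuous measures: PRU, LTA at 5 µM and at 20 µM ADP, VASP-PRI, that is 4.
- HPR definitions: 4, or 5 if both PRU cut-offs (208 and 235) are used.
- Level: two-sided 0.05 per test. Evaluable patients: 16 per arm (sample size section).

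**Assumptions.** All pairs are tested at all five times. The documents give no correlations between assays or between times, so a range is used.

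**Step 1: number of secondary tests**
- Continuous: 6 × 5 × 4 − 1 primary = 119.
- HPR: 6 × 5 × 4 = 120.
- Total: 119 + 120 = 239. With both PRU cut-offs, 119 + 150 = 269. With one HPR test per platform, 119 + 90 = 209.
- If only overall four-group tests are run: 4 × 5 + 4 × 5 = 40, or 4 × 5 + 5 × 5 = 45 with both cut-offs.
- Genotype, within-group and pre-randomization comparisons would come on top.

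**Step 2: how many are null if loading dose and timing make no difference (A = B = C)**
- Continuous: 3 × 5 × 4 − 1 = 59. HPR: 3 × 5 × 4 = 60. Total: 119.
- A versus B alone, continuous: 1 × 5 × 4 = 20.

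**Step 3: the independence figure, as an upper reference only**
- 59 tests: 1 − 0.95^59 = 0.95. 20 tests: 1 − 0.95^20 = 0.64.
- These overstate the risk, because the tests share patients, visits and pathway.

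**Step 4: simulation with correlation.** Null trials were simulated with 16 patients per arm, 4 assays × 5 times and two-sided t tests at 5%. The correlation across both assay and time is the product of the two assumed values. Entries are the chance of at least one p < 0.05.

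| Correlation between assays / times | 59 tests among A, B, C | 20 tests, A vs B |
|---|---|---|
| 0.9 / 0.8 | 46% | 23% |
| 0.7 / 0.5 | 74% | 43% |
| 0.5 / 0.3 | 85% | 54% |

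Repeated runs differ by a percentage point or two, hence the ranges of about 45–86% and 22–55%. The mean number of false positives among the 59 is about 3 in every row (59 × 0.05 = 2.95). In the top row the median is 0: high correlation gives fewer trials with a false positive, but more of them in each such trial.

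**Step 5: adding HPR (119 null tests).** With one common correlation for assays and times, an assumed HPR prevalence of 30% and 16 or 20 per arm, the chance is 49–51% at 0.9, 72–76% at 0.7 and 85–88% at 0.5. The mean number of false positives in simulation is about 4.0 to 4.7, below 119 × 0.05 = 5.95 because Fisher's exact test is conservative.

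**The case against.** The strongest reply is that this is a small pharmacodynamic study with one fully specified primary comparison. Group pair, assay, hour and method are all fixed, and everything else is called secondary. The documents do not say that a secondary result will support a confirmatory claim. That stands, and it limits the point. A reader might infer that the trial's main conclusion is exposed. It is not, because the primary is a single pre-specified test at 5%.

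Second, the plan does not commit to about 240 tests. Comparison in all four groups can be read as one overall test per measure and time, which gives 40 to 45. That also stands. But an overall test that includes group D cannot by itself answer the loading-dose or timing question. Pairwise tests would have to follow, and the plan neither gates them nor exempts them from the 5% label.

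Third, a reader might join the count of 239 to the case of no loading-dose or timing effect and conclude that false positives are almost certain. The documents do not support this. Half of the tests involve the group that stays on ticagrelor, so they are not null in that case, and near-certainty holds only under independence.

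Fourth, the probabilities depend on correlations that the documents do not give. This is true. In the high-correlation case the chance is just under one half among A, B and C and about a quarter for A versus B, so it is not always more likely than not. Both figures are still well above 5%.

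**Conclusion.** The point holds for secondary claims only. Followed as written, the rule lets unranked secondary comparisons be reported as statistically significant with no control of error. Among A, B and C, the 59 continuous secondary tests carry a chance of about 45% to 86% of at least one false significant result. For the 20 A versus B tests the chance is about 22% to 55%.

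These figures rest on three assumptions: pairwise testing at all five post-randomization times, 16 evaluable patients per arm, and the stated correlation range. The count of 239 (209 to 269, depending on how HPR is tested) rests on the first of these and is not a figure in the plan.

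A reader might also infer that timing must be the one key secondary question. The documents do not settle that: the Study aim names loading dose and CYP2C19 status, while timing is raised in the Background and through the design of group B.

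**What to change.** In the Statistical analysis plan, limit the statistically significant rule to the primary comparison (A versus C, PRU at 48 hours). State that all secondary comparisons, including HPR rates and the effect of CYP2C19 status, are exploratory and will be reported as estimates with 95% CIs, with any p values marked nominal.

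Optionally, the sponsor may name one key secondary before analysis, with a single pair, measure and time, tested at two-sided 5% only if the primary succeeds. Testing in this fixed order takes no alpha or power from the primary. The choice of question is the sponsor's.

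The cost is wording only: no patients, samples or visits change. The downside is that secondary results other than a named key secondary can no longer be reported as statistically significant.
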